**Justification of Sample Size:**

The sample size objective for the study is to recruit  $N = 280$  women who will be randomly assigned to the *BSM* or attention control study groups at a 1:1 ratio (140 per group). This objective provides 80% power ( $\alpha = 0.05$ , two-sided) to detect a standardized mean difference (Cohen's  $d$ ) of 0.39 or more between the *BSM* and attention control groups. It also provides 80% power to detect an odds ratio of 2.5 or more in exclusive BF between the two groups, assuming that the exclusive BF rate of the control group will be 10% higher than the national population rate in 2017 at 6, 9, 12, 18, and 24 weeks. These calculations account for "loss to follow-up" as high as 25% at 24 weeks, despite the substantially lower attrition (6%) in our pilot study. Based on our pilot study, we approached 78 women to meet our sample size of 60, with a failed screening rate of 25%. Thus, we intend to approach 374 women, which is 25% higher than our proposed study sample to meet our sample size. We anticipate that approximately 70% of the study sample will be WAHS or HHC patients.

In the pilot study, RM-ANCOVAs (with the baseline value of a measure as the covariate) revealed standardized mean differences larger than  $d = 0.39$  for the "main effect" of the intervention on BNP intensity ( $d = 0.45$ ), pain severity ( $d = 0.60$ ), cumulative pain ( $d = 0.64$ ), and BF self-efficacy ( $d = 0.48$ ) across the 1-, 2-, and 6-week time points. For BNP interference, the value of  $d$  was 0.39 at week 1, but smaller at weeks 2 and 6. Furthermore, the odds of exclusive BF in the intervention group are 2.9 times higher than the control group at 6 weeks, which is also higher than the hypothesized OR = 2.5. Therefore, we are confident that the sample size goal will be sufficiently powered to detect intervention effects on key variables for SA1 and SA2. Finally, the sample size estimate does not reflect our plans to conduct analyses based on repeated measurement of outcome variables at the 1, 2, 3, 6, 9-, 12-, 18-, and 24-week time points (due to the dearth of information regarding 24-week outcomes). Generally, the inclusion of data for an outcome variable across additional time points marginally enhances statistical power, especially for testing "main" and "interaction" effects of intervention and time.

**Enrollment of Employees:**

Employees or Hartford Hospital Employees may be recruited if they receive clinical care from Women's Ambulatory Center, or private obstetric care at Hartford Hospital or UConn Health Center. We will not recruit any women who report to key personnel.

**Enrollment of Key Personnel, Spouses or Dependents/Relatives:**

We will not recruit key personnel, spouses of key personnel, or dependents/relatives of any key personnel.

**For EACH Participant Population Describe Screening Procedures, if applicable**

The proposed RCT will be conducted to test the effect of the *BSM* intervention vs. an attention control group on BNP, BF exclusivity and duration, BF self-efficacy and maternal well-being to 24 weeks (Figure 4). Participants at baseline will complete assessments, quantitative sensory testing, and provide buccal cell and/or blood samples for assessment of select pain sensitivity SNPs and DNA methylation and again at 6 and 24 weeks at our research sites. At 1, 2, 3-, 9-, 12-, and 18-weeks participants will complete assessments via smartphone text and the UConn Health Research Electronic Data Capture (UConn REDCap) links, <https://health.uconn.edu/clinical-researchcenter/> when women shelter at home. If a participant does not have a smartphone, the study will provide a smartphone for them to receive texts and text links. All participants will receive educational material regarding infant development and age-appropriate play at 4, 8, 12, 16, 20, and 24 weeks to maintain contact and sustain engagement in the study. Following UConn Institutional Review Board approval, all recruitment and initial data collection will occur in collaboration with our clinical partners, at the UConn Health Center, a 234-bed tertiary care academic hospital delivering 700 infants a year with 560 women initiating BF; the Women Ambulatory Services at Hartford Hospital (HH), delivering 1000 infants a year with 800 women of diversity initiating BF (see letters of support) and women receiving private obstetric care at Hartford Hospital, delivering 2900 infants a year with 2320 initiating BF.

Prior to launch of the study, all research personnel will receive training on human subjects' research, HIPAA, and biological safety, handling and transportation. The study designated graduate assistants will develop a study binder of all protocols and each role will be established so that appropriate blinding procedures can be maintained throughout the study duration. [name] and the project manager will train all research personnel (graduate assistants, research assistants, and peer counselors) on the standardized intervention, scripts, protocols for women who need referrals or follow-ups for BF support or maternal well-being, documentation of schedule data collection visits, and establish weekly research team meetings.

**Anticipated Study Time Frame:**

Recruitment will begin in October 2021 and continue through December 2024.

Research activity/Quarter	Year 1				Year 2				Year 3				Year 4			
	1	2	3	4	1	2	3	4	1	2	3	4	1	2	3	4
Start-up, team, training, IRB approval	X	X														
Subject enrollment in Y1=50, Y2=110, Y3=110, Y4=10; Data collection; Data quality management		X	X	X	X	X	X	X	X	X	X	X				
Complete follow-up			X	X	X	X	X	X	X	X	X	X	X	X	X	X
Presentation at conferences				X				X		X					X	X
Submission of protocol and interim analysis article					X				X				X			
Complete database; Final analyses; Grant preparation, Final report					X		X				X	X	X	X	X	X

**Design, Procedures, Materials and Methods:**

The proposed RCT will be conducted to test the effect of the *BSM* intervention vs. an attention control group on BNP, BF exclusivity and duration, BF self-efficacy and maternal well-being to 24 weeks

(Figure 4). Participants at baseline will complete assessments, quantitative sensory testing, and provide buccal cell and/or blood samples for assessment of select pain sensitivity SNPs and DNA methylation and again at 6 and 24 weeks at our research sites. At 1, 2, 3-, 9-, 12-, and 18-weeks participants will complete assessments via smartphone text and the UConn Health Research Electronic Data Capture (UConn Health REDCap) links,

<https://health.uconn.edu/clinical-researchcenter/> when women shelter at home. If a participant does not have a smartphone, the study will provide a smartphone for them to receive texts and text links. The consent will inform the participant that if the phone is lost before the participant withdraws or attends the 6-month research visit, \$75 will be deducted from the remuneration for their 6-month visit. All participants will receive educational material regarding infant development and age-appropriate play at 4, 8, 12, 16, 20, and 24 weeks to maintain contact and sustain engagement in the study. Following UConn Institutional Review Board approval, all recruitment and initial data collection will occur in collaboration with our clinical partners, at the UConn Health Center, a 234-bed tertiary care academic hospital delivering 700 infants a year with 560 women initiating BF; and the Women Ambulatory Services at Hartford Hospital (HH), delivering 1,000 infants a year with 800 women of diversity initiating BF (see letters of support) women receiving private obstetric care at Hartford Hospital, delivering 2900 infants a year with 2320 initiating BF.

Prior to launch of the study, all research personnel will receive training on human subjects' research, HIPAA, and biological safety, handling and transportation. The study designated graduate assistants will develop a study binder of all protocols and each role will be established so that appropriate blinding procedures can be maintained throughout the study duration. [name] and the study Project Manager will train all research personnel (graduate assistants and peer counselors) on the standardized intervention, scripts, protocols for women who need referrals or follow-ups for BF support or maternal well-being, documentation of schedule data collection visits and establish weekly research team meetings. [name] and the Project Manager will conduct internal audits every three months to ensure fidelity in recruitment and procedures.

Table 1: Timeline of procedures

Week	Day	Measure	Location	Time	Compensation
Prenatal visit	Recruitment	Study flyer, Breastfeeding Basic Information	HH, WAHS, UCHC prenatal clinic	5 min	\$0
0	Recruitment	Initial Screen	Hospital/ Smart phone	5 mins	
0	Baseline Assessment	Consent 
 
Verification of CLC evaluation of breastfeeding
 
Buccal cell swabs and/or blood collection (15 ml or 3 teaspoons)
 
QST
 
Questionnaires
 
Demographics
 
Breastfeeding Specific Factors: Maternal and Infant Breastfeeding History
 
	Hospital	1 hr Links will be shared for individuals to	\$25 UConn Greenphire Gift Card or ecard

		
 
• Breastfeeding Log (BL) 
 
◦ MAIBB-R
 
◦ Algorithm
 
 
 
• Breastfeeding Battery (BB) 
 
◦ BSES-SF
 
◦ Ongoing Breastfeeding Assessment
 
 
 
• Pain Interpretation Scales (PIS) 
 
◦ Coping Strategies Questionnaire
 
◦ McGill Pain Questionnaire
 
◦ Brief Pain Inventory
 
◦ Visual analogue scale
 
 
 
• Maternal Well-Being (MWB) 
 
◦ NINR CDEs (Anxiety, Sleep, Fatigue, Perceived Stress Scale, Index of Self-Regulation, Self-Efficacy for Managing Chronic Illnesses Scale, Global Health)
 
◦ EPDS
 
◦ Karitane Parenting Confidence Scale
 
 
 
		complete on their own	
1	Days 1-5	Intervention Group ONLY: BL: 1 entry/ day Texts 2 times/ week breastfeeding coaching with links to Breastfeeding Modules 1-3 Maternal/Infant Care Modules 1-2	Personal computer/ smartphone	5 mins per entry  10 mins/ module	
	Days 1-5	Control Group ONLY: Texts 2 times/ week with links to Maternal/Infant Care Modules 1-2	Personal computer/ smartphone	10 mins/ module	
	Day 5	Both Groups: BB, PIS, MWB Control Group only: BL	Personal computer/ smartphone	10 mins	\$25 UConn Greenphire Gift Card or ecard
2	Days 8-12	Intervention Group ONLY: BL: 1 entry/ day Texts 2 times/ week breastfeeding coaching with links to Breastfeeding Modules 4-6 Maternal/Infant Care Modules 3-4	Personal computer/ smartphone	5 mins per entry  10mins/ module	
	Days 8-12	Control Group ONLY: Texts 2 times/ week with links to Maternal/Infant Care Modules 3-4	Personal computer/ smartphone	10 mins/ module	
	Day 12	Both Groups: BB, PIS, MWB Control Group only: BL	Personal computer/ smartphone	10 mins	\$25 UConn Greenphire Gift Card or ecard
3	Days 15-19	Intervention Group ONLY: BL: 1 entry/ day	Personal computer/	5 mins per entry	

		Texts 2 times/ week breastfeeding coaching with links to Breastfeeding Modules 7-9 Maternal/Infant Care Modules 5-6	smartphone	10mins/ module	
	Days 15-19	Control Group ONLY: Texts 2 times/ week with links to Maternal/Infant Care Modules 5-6	Personal computer/ smartphone	10 mins/ module	
	Day 19	Both Groups: BB, PIS, MWB Control Group only: BL	Personal computer/ smartphone	10 mins	\$25 UConn Greenphire Gift Card or ecard
Weeks 4-6	Days 21-40	Intervention Group ONLY: BL: 1 entry/ day Texts 2 times/ week breastfeeding coaching with links to Maternal/Infant Care Modules 7-12	Personal computer/ smartphone	5 mins per entry 5 mins/ module	
	Days 21-40	Control Group ONLY: Texts 2 times/ week with links to Maternal/Infant Care Modules 7-12	Personal computer/ smartphone	5 mins per entry	
Week 4	Day 26	Both Groups Infant development and play modules at 4 weeks	Personal computer/ smartphone	10 mins	
Week 6	Day 40	Both Groups: 
 
• Buccal cell swabs and/or blood collection (15 ml or 3 teaspoons)
 
• QST
 
• BL
 
• BB, PIS, MWB
 
• Audio taped semi-structured interview: Reflection on participating in the study and the impact on their breastfeeding outcomes
 
	Clinic, smartphone	60 mins  15 mins	\$50 UConn Greenphire Gift Card or ecard
Week 8	Day 54	Both Groups Infant development and play modules at 8 weeks	Personal computer/ smartphone	10 mins	
Week 9	Day 61	Both Groups: BB, PIS, MWB, BL	Personal computer/ smartphone	10 mins	\$35 UConn Greenphire Gift Card or ecard
Week 12	Day 82	Both Groups: BB, PIS, MWB, BL Infant development and play modules at 12 weeks	Personal computer/ smartphone	10 mins	\$35 UConn Greenphire Gift Card or ecard
Week 16	Day 110	Both Groups Infant development and play modules at 16 weeks	Personal computer/ smartphone	10 mins	
Week 18	Day 122	Both Groups: BB, PIS, MWB, BL	Personal computer/ smartphone	10 mins	\$35 UConn Greenphire Gift Card or ecard
Week 20	Day 138	Both Groups Infant development and play modules	Personal computer/	10 mins	

		at 20 weeks	smartphone		
Week 24	Day 166	
Both Groups:
 
 
• Buccal cell swabs and/or blood (15 ml or 3 teaspoons) collection
 
• QST
 
• BL, BB, PIS, MWB
 
• Audio taped semi-structured interview: Reflection on participating in the study and the impact on their breastfeeding outcomes
 
• Infant development and play modules at 24 weeks
 
	
Clinic, Interview, smartphone
	
60 mins 15 mins
	\$75 + \$25 bonus UConn Greenphire Gift Card or ecard

### Procedures and Data Collection at each Time Point.

At baseline we will collect demographic information, pain and coping scales, BF measures, maternal well-being symptoms, pain, BF and maternal self-efficacy scales, and quality of life health status.

Subsequently, quantitative sensory testing will be performed on the non-dominant forearm and a buccal cell and/or blood samples will be obtained for analysis of selected pain sensitivity SNPs and DNA methylation. All buccal cell swabs and/or blood (15 ml or 3 teaspoons) samples will be labeled with the participants' identification number. Blood will be kept at room temperature on the clinical unit and during transport, and buccal swabs will be stored in a freezer on the clinical unit at -20 degrees Fahrenheit, until transported to the SON Biobehavioral Lab (BBL) for processing and storage.

Study questionnaires will be administered via electronic surveys using UConn Health REDCap v11. Participant will access the UConn Health REDCap link before discharge to access and view texts, web links, and the video modules on either handheld device (e.g., smartphone, iPad) or computer desktop/laptop. All participants will receive an encrypted text (via UConn Health REDCap with an embedded link from Twilio) or an email per their preference with the study measures via UConn Health REDCap v11. After the initial surveys are completed, participants will be asked to contact a member of the research team to register their Greenphire incentive card. A member of the research team will complete the Greenphire form which includes social security number (field is encrypted), address, email and phone number to initiate the first incentive payment. The PROMPT study does not retain participant's social security number or address in our records. If the participant does not have a social security number, ecards will be provided by UConn School of Nursing business office. The team member will also refer the participant to WAHS and Outpatient Lactation scheduler or the UConn Health scheduler for the 6 week follow up visit.

**Intervention Administration.** Each group will receive a link to the eight video modules between 3-5 minutes long that address a different topic. During the first week, the appropriate link to the first video to the BSM intervention and attention control group will be sent. Intervention fidelity will be addressed using Resnick et al's framework of design, training, delivery, receipt, enactment, which will be continuously assessed throughout the study duration. Design fidelity will be applied through a standardized intervention with scheduled interactive texts, text-based daily BF journals and links to modules. Training of the interventionist(s) will be assessed routinely by [name] through simulated scenarios and practice sessions using texting and phone scripts. Evidence of treatment will include participants' response to bi-weekly texts and targeted lactation support based on galactogenesis and lactation milestones. The research team will monitor intervention fidelity by using the UConn Health

REDCap feature that will allow research team to view the date, time, length, and number of times the participant accesses each module and completes the daily BF journal. Our Project Manager, blinded to initial randomization, will coordinate the research team to send participants texts, follow-up phone calls, and emails as needed, at 1, 2, 3, 9, 12, and 18 weeks to encourage completion of the modules and for BSM intervention, address any BF concerns. After the first week, depending on the participant's preference, encrypted text messages, phone calls and/or emails will be made by the research team to encourage BF data completion.

**Data Collection during Follow up.** After discharge, both groups will receive an encrypted text via UConn Health REDCap with embedded links from Twilio, a cloud communications platform and a back-up archive feature. The follow-up measures at 1, 2, 3, 9, 12, and 18 weeks (Figure 4) include the participants' weekly BNP, pain coping, BF exclusivity, ongoing BF assessment, BF algorithm and maternal assessment of infant BF behaviors, self-efficacy scales (pain, BF, and maternal), maternal well-being assessments, and perceived well-being scales. Completion of the measures will take about 30 minutes. Our statistician team at weekly meetings will identify any missing data to facilitate contact of participants to complete surveys. At 6 and 24 weeks, participants will complete the above measures and repeat quantitative sensory testing and provide buccal cell and/or blood samples for selecting pain sensitivity SNPs and DNA methylation at our clinical locations. Completion of the measures will take about 60 minutes. At Weeks 4, 18 and 20, participants will receive a prompt in their modules to provide their 6 week and 6-month research appointment day and time. If participants do not provide a date and time, research personnel will reach via text (up to three times) to schedule the appointment.

**Blinding.** We will employ blinding whenever possible. The PI and all the research team members involved in data collection or analysis will be blinded to the randomization of the participants, and some of the research team to the group assignment of participants. The statisticians, project manager and graduate assistant will not be blinded to study assignment and ongoing data collection. Research team personnel will follow a strict script to refrain from discussing participant activities, and by using the data management graduate assistant (unblinded) to coordinate assigned condition activities and data collection and analysis. All participants will be assigned a study number, which will be used to track the study measures and buccal cell and/or blood samples. De-identified data with dummy-codes for assigned condition will be entered into the study database to allow blinded data analysis. Blinding was successfully employed during our pilot study.

**Participant Retention.** Participants will receive progressive monetary incentives, and to retain trust, the participants in both groups will receive monthly text links to normal infant development and age-appropriate play modules.

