The randomization algorithm will be implemented in REDCap using published code that operates within "R" statistical software. An interface between REDCap and R software will be created by the project statisticians as a "Shiny app" within the RStudio development environment. The resulting R Shiny app will allow the project's recruitment staff to enter the predictive characteristics for a new participant, will compare the new participant's mix of characteristics to those of current participants, and will produce a "blinded" study group assignment for the new participant. The blinded group assignment will be presented to the recruitment staff as one of four letters: A, B, C, or D. That letter will then be entered into REDCap as the new participant's record is set-up. REDCap will be programmed to link each of the four letters to a study group (two letters for the BSM group and two others for the control group). Only the project statisticians, the project manager and the graduate assistant will know the correspondence between letters and group assignments. Four letters (and a corresponding study "arm" for each one) will be used to make it more difficult for recruitment staff to decipher which letters link to specific study groups and, therefore, to foster the likelihood that blinding to group assignment will be maintained throughout the project.

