### **Data Analysis and Management**

All data will be entered into a password-protected database stored on a firewall-protected server that is maintained by UConn. We will use the existing structure of data management established with our pilot study. The protocols established for trialing and monitoring UConn Health REDCap will be strictly followed. We have designed data collection forms to check for missing data in real-time to avoid incomplete data and routinely monitor data input. Our Project Manager, working with the statisticians, will prepare a weekly data summary, which will be reviewed during weekly team meetings.

**Statistical Analysis Overview.** Prior to undertaking statistical modeling, descriptive statistics will be determined for the study's key independent and dependent variables in order to evaluate the effectiveness of randomization, to check distributional assumptions (such as normality), to identify potential outlying observations, and to obtain preliminary insights into homogeneity versus heterogeneity of variance for outcome measures. Analyses will be conducted using SAS 9.4 and R^194.

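### The blinding statements conflict, and the blinded analysis claimed is not secured for SA1 and SA2 because no analyst without the allocation key is named

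*Combined protocol and SAP*

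**What the plan says.** The Blinding paragraph (under Procedures and Data Collection at each Time Point) makes a general claim: "The PI and all the research team members involved in data collection or analysis will be blinded to the randomization of the participants". The sentence after it reads: "The statisticians, project manager and graduate assistant will not be blinded to study assignment and ongoing data collection". The paragraph also gives a coordinating task to an unblinded person, "using the data management graduate assistant (unblinded) to coordinate assigned condition activities and data collection and analysis", and closes by saying that dummy codes for condition in the database will permit a blinded analysis.

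Enrollment and Randomization describes the masking of recruitment staff, who see one of four letters, two per arm. It then says who can read the letters: "Only the project statisticians, the project manager and the graduate assistant will know the correspondence between letters and group assignments".

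The Intervention Administration paragraph says of one of those roles: "Our Project Manager, blinded to initial randomization, will coordinate the research team to send participants texts".

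Two statements place the unblinded roles close to the accruing data. In Data Collection during Follow up: "Our statistician team at weekly meetings will identify any missing data to facilitate contact of participants to complete surveys". In Data Analysis and Management: "Our Project Manager, working with the statisticians, will prepare a weekly data summary, which will be reviewed during weekly team meetings".

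**The concern.** A blinded analysis protects a trial only if the person making analytic choices cannot tell which arm is which. Dummy codes achieve that when the analyst does not hold the key. Here the key is given to the project statisticians as a group, and they are the only people the plan presents as likely to fit the SA1 and SA2 models.

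Two things are at stake. First, some choices are left until the data have been seen, and an analyst who knows the arms and expects the intervention to help can drift towards that result without intending to. Second, a final report that cites this protocol for a blinded analysis would claim something the described arrangement does not provide. The conflicting description of the project manager adds a practical problem: staff reading different sections would come away with different ideas of who may be told what.

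**Working it through.** The plan gives no figure on this point, so the check is textual.

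**1. Status of each role.**

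| Role | Blinding paragraph, general sentence | Blinding paragraph, next sentence | Enrollment and Randomization | Intervention Administration |
|---|---|---|---|---|
| Statisticians | blinded, if they analyse | unblinded | hold the key | not stated |
| Project manager | blinded, if involved in data collection | unblinded | holds the key | blinded |
| Graduate assistant | blinded, if involved in data collection or analysis | unblinded | holds the key | not stated |
| PI | blinded | not listed as unblinded | not a key-holder | not stated |
| Recruitment staff | blinded, if they collect data | not listed as unblinded | see letters only | not stated |

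The conflict is confined to the first three rows. For the project manager it runs across three sections.

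**2. Can the conflicts be read away?** The two Blinding sentences could be a rule followed by an exception. That removes the formal contradiction, but the exception then covers the statisticians, who are the people the claim of blinded analysis most needs to cover. For the project manager, blinding to the initial randomization could mean only that this person does not make the assignment. Enrollment and Randomization nevertheless gives the project manager the key, so the blind would have no content.

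**3. Who analyses SA1 and SA2?** The Approach section describes the team statistician's expertise as covering design, data handling and analysis. No other analyst is named for these aims. That key-holders will fit the models is therefore an inference, though the only one the documents offer. SA4 differs: its methylation data go to another team member working with an outside institute, and neither is named as a key-holder.

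**4. What is left to judgement?** Three steps in the SA1 text were checked.
- *Dropping the interaction.* A stated rule, triggered by non-significance. Not open.
- *Adding demographic covariates.* To be done where needed, with no list of variables and no criterion. Open.
- *Outliers.* Diagnostics will identify influential observations, but no response is given. Open as to what follows.

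BF self-efficacy and maternal well-being in SA2 are to follow the SA1 approach, so the open points carry over to them.

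**5. What is not affected?** Blinding does not enter the sample-size calculation. The 280 women, the two-sided alpha of 0.05 and the 80% power stand as they are. The visual analogue scale and Brief Pain Inventory are completed by the women through REDCap links, so unblinded staff do not score them.

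**The case against.** The strongest reply is that the plan is open about its three unblinded roles and promises blinding only where possible. The PI and the other data collectors are described as masked, recruiters see only letters, a script restricts discussion, and the main pain outcomes are self-reported. It is also not written anywhere that key-holders will run the SA1 and SA2 models. All of this stands, and it limits the point. It does not supply a key-free analyst or reconcile the sections.

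A reader might go further in three ways that the documents do not support.

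- *That there is no blind at all.* Disclosing three unblinded roles does not undo the masking described for the PI, recruiters and remaining data collectors.
- *That unblinded staff decide whom to follow up.* The statisticians flag missing data. Post Enrollment Exclusion Criteria sets one sequence for all participants: a text reminder, REDCap pushes, a call or email if needed, contact at the next time point, and removal after three consecutive missed points. Protection against Risk limits reminders in a similar way. Only the use of calls and emails is discretionary.
- *That decoded letters would bias the sensory testing.* No section says that recruiters keep the letters or perform the 6- and 24-week tests. The SA1 to SA3 analysis text plans no between-arm comparison of sensory testing. Any decoding probability would depend on an assumed number of disclosures and would say nothing about the analysts.

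**Conclusion.** The point holds in a limited form. The blinding statements in Enrollment and Randomization, Intervention Administration and Blinding contradict one another, and the blinded analysis claimed is not secured for SA1 and SA2. Three roles are affected, and two analytic choices (demographic covariates and the response to outliers) remain open to people who probably know the arms.

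The documents do not allow the resulting bias to be quantified, and there is no evidence that it has occurred. The conclusion assumes that the project statisticians, all described as knowing the key, will run SA1 and SA2. If a key-free analyst is already in place, what remains is to say so and correct the text.

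**What to change.** 1. **Reconcile the text.** Put one list in the Blinding paragraph showing each role as blinded or unblinded, with the project manager unblinded, and bring Enrollment and Randomization and Intervention Administration into line with it.
2. **Separate two tasks among the existing project statisticians.** One holds the key and runs the randomisation app. Another, without the key, carries out SA1 and SA2 on dummy-coded data. The codes must not be traceable to the four letters. Models, covariates and outlier handling are fixed and signed before the codes are linked to arms.
3. **If that cannot be done,** for example because every statistician already knows the allocations, withdraw the claim of blinded analysis. Fixing and signing the same analysis decisions in advance would still be worthwhile.

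The cost is a reassignment of duties and edits to three sections. The small downside is that the analysing statistician cannot also service the randomisation app. Sample size, visits and outcome measures do not change.
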